8.4.3.2. Exposure During Breastfeeding

Scenarios of exposure during breastfeeding must be reported, irrespective of the presence of an associated SAE, to Pfizer Safety within 24 hours of the investigator's awareness, using the CT SAE Report Form. An exposure during breastfeeding report is not created when a Pfizer drug specifically approved for use in breastfeeding women (eg, vitamins) is administered in accord with authorized use. However, if the infant experiences an SAE associated with such a drug's administration, the SAE is reported together with the exposure during breastfeeding.

8.4.3.3. Occupational Exposure

An occupational exposure occurs when, during the performance of job duties, a person (whether a healthcare professional or otherwise) gets in unplanned direct contact with the product, which may or may not lead to the occurrence of an AE.

An occupational exposure is reported to Pfizer Safety within 24 hours of the investigator's awareness, using the CT SAE Report Form, regardless of whether there is an associated SAE. Since the information does not pertain to a subject enrolled in the study, the information is not recorded on a CRF; however, a copy of the completed CT SAE Report Form is maintained in the investigator site file.

8.4.4. Medication Errors

Other exposures to the investigational product under study may occur in clinical trial settings, such as medication errors.

Safety Event	Recorded on the CRF	Reported on the CT SAE Report Form to Pfizer Safety Within 24 Hours of Awareness
Medication errors	All (regardless of whether associated with an AE)	Only if associated with an SAE

8.4.4.1. Medication Errors

Medication errors may result from the administration or consumption of the investigational product by the wrong subject, or at the wrong time, or at the wrong dosage strength.

Medication errors include:

- Medication errors involving subject exposure to the investigational product;
- Potential medication errors or uses outside of what is foreseen in the protocol that do or do not involve the participating subject.

Other examples include, but are not limited to:

- The administration of expired investigational product;
- The administration of an incorrect investigational product;
- The administration of an incorrect dosage;
- The administration of investigational product that has undergone temperature excursion from the specified storage range, unless it is determined by the sponsor that the investigational product under question is acceptable for use.

Such medication errors occurring to a study subject are to be captured on the medication error page of the CRF, which is a specific version of the AE page.

In the event of a medication dosing error, the sponsor should be notified immediately.

Whether or not the medication error is accompanied by an AE, as determined by the investigator, the medication error is recorded on the medication error page of the CRF and, if applicable, any associated AE(s), serious and nonserious, are recorded on an AE page of the CRF.

Medication errors should be reported to Pfizer Safety within 24 hours on a CT SAE Report Form **only when associated with an SAE**.

8.5. Medical Device Complaint Reporting Requirements

All medical device complaints, regardless of whether the medical device complaint is associated with an AE, will be reported by a member of unblinded site staff as described in the IP manual. This includes potential incidents or malfunctions associated with the use of a medical device product. An incident or malfunction is an event that might have led to death or serious deterioration in health, or if it occurred again might lead to death or serious deterioration in health.

Pfizer is to be notified of all medical device complaints within 24 hours of the investigator's awareness of the event.

9. DATA ANALYSIS/STATISTICAL METHODS

The methodology for summary and statistical analyses of the data collected in this study is outlined here and further detailed in a statistical analysis plan (SAP), which will be maintained by the sponsor. The SAP may modify what is outlined in the protocol where appropriate; however, any major modifications of the primary endpoint definitions or their analyses will also be reflected in a protocol amendment. Supplemental analyses of the primary, secondary, immunogenicity, and safety data may be performed as required for local regulatory jurisdictions (for example, analyses by age, sex, ethnicity, risk status prior to vaccination) and will be prespecified in the SAP.

The SAP will be finalized prior to any analyses being undertaken.

9.1. Sample Size Determination

This study is placebo-controlled, event-driven, and randomized with a 1:1 randomization ratio between subjects receiving *C difficile* vaccine and placebo.

With assumptions of a true adjusted VE of 66.5% after 3 doses of investigational product, 66 first primary CDI cases (meeting case definition 1 in the per-protocol-3 population [Section 2.1.1](#) and [Section 9.2.1](#)) will provide 89.8% power to conclude true VE of >20%, taking into consideration 3 interim analyses ([Section 9.5](#)) during the study.

The early efficacy stopping boundaries are based on a GS design⁶⁵ utilizing a single-binomial distribution, conditional on a total of 66 cases, assuming true VE of 66.5%, with 3 interim analyses at 30, 40 and 50 cases.⁶⁵ The same gamma[-2] alpha spending function that was used for the original statistical design is also used for this modified statistical design.

As this is an event-driven and GS study, the total enrollment number may vary depending on the assumptions of incidence rate of the primary endpoint, true VE, and potential early stop for efficacy or futility.

Update as Part of Amendment 2 (January 2019):

Based on the ongoing blinded review of pooled primary CDI events, the annual CDI incidence rate in the placebo group may be different from the assumed rate in the power calculation during the initial study design. Additional enrollment may be needed in order to maintain the study power of 90% (106 first primary CDI cases in the final analysis) to reject the null hypothesis of $VE \leq 20\%$. Assuming a true VE of 60% after 3 doses of investigational product and the true annual CDI rate in the placebo group of 0.552% to 0.516%, which is 8 to 14% lower than the previously assumed 0.6%, an additional 1369 to 2566 subjects may be needed to ensure the required number of first primary CDI cases.

In light of this, it is planned to enroll approximately 1700 additional subjects, giving a total of approximately 17,476 subjects. The pooled primary CDI event rate for the total population will continue to be monitored by the study team in a blinded manner and a further adjustment to enrollment may be required.

Update as Part of Amendment 4 (July 2020):

The statistical design is being modified to perform all the analyses with fewer cases than originally planned. Two (2) additional interim analyses will be included based on the estimated disease rate from the blinded data review, and the assumption regarding true VE is modified to 68%, and is further adjusted to 66.5% after 3 doses of investigational product because of the impact of actual specificity (99.1%) and sensitivity (95.7%) of Pfizer's cell cytotoxicity neutralization assay.⁶⁶

The pooled primary CDI event rate for the total population will continue to be monitored by the study team in a blinded manner and a further adjustment to enrollment may be required.

As specified in [Section 3.1](#), the pooled primary CDI event rates in different age groups, inclusion criteria subgroups, CCI⁶¹ subgroups, and other baseline factors will be monitored in a blinded manner. Once the specified minimum numbers in each age group have been achieved, if a substantially higher pooled CDI event rate is observed in some subgroups, the intention may be to stop enrollment in lower-risk subgroups and complete enrollment with the higher-risk subgroups thereafter. This is mainly to help to achieve the targeted total number of first primary cases in a timely manner. As none of the potential adjustments will be based on the observed VE of the ongoing study, and the targeted total number of first primary CDI cases will remain the same, the distribution of the test statistic for the primary endpoint under the null hypothesis will not be affected and no alpha adjustment will be required.

For the second primary hypothesis test, it is expected that more than 66 cases for the final analysis will occur after 2 or more doses because of the nature of the endpoint. Any additional first primary CDI cases occurring in the interval between Doses 2 and 3 will result in greater than 90% power to conclude true VE of >20% after 2 or more doses of vaccine assuming the vaccine first successfully demonstrates VE of >20% following 3 doses of vaccine.

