9.2.1. Analysis of the Primary Endpoints

VE is defined as $VE = 100 \times (1 - IRR)$, where IRR is the infection rate ratio, the calculated ratio of first primary CDI incidence between the *C difficile* vaccine group and the placebo group. VE_i will be evaluated separately after 3 and after 2 doses. The 2 primary efficacy hypotheses are (in order of fixed-sequence testing):

1. $H_{03}: VE_3 \leq 20\%$ vs $H_{a3}: VE_3 > 20\%$, and
2. $H_{02}: VE_2 \leq 20\%$ vs $H_{a2}: VE_2 > 20\%$.

where H_{0i} and H_{ai} represent null hypothesis and alternative hypothesis, and VE_i ($i = 2, 3$) represents VE after at least 2 doses and after all 3 doses, respectively. For subjects with multiple primary CDI cases, only the first primary case will contribute to the VE calculation in each hypothesis test.

The primary efficacy hypotheses will be tested by a 1-sided test for $VE > 20\%$ by a fixed-sequence testing procedure, with testing order of H_{03} followed by H_{02} using the approach described in Chan and Bohidar,⁶³ accounting for follow-up time after vaccination. Statistical inference will be based on the lower alpha-adjusted confidence interval (CI) for VE_3 , and VE_2 .

If the study continues after all 3 of the interim analyses, once 66 first primary cases after 3 doses have accumulated for the final analysis, the hypothesis test H_{03} will be performed first, and the null hypothesis H_{03} will be rejected if there are 20 or fewer cases observed in the *C difficile* vaccine group (corresponding to a 2-sided lower bound of 96.4% exact CI $> 20\%$), assuming equal follow-up times. The lower bound of the 2-sided 96.4% exact CI corresponds to $\alpha = 0.018$ (one-sided) used for final testing in a GS design with a gamma(-2) efficacy boundary. Only if the hypothesis H_{03} is rejected, then hypothesis testing for H_{02} will be performed, at the same significance level for VE_2 for the final analysis. The statistical success criterion for H_{02} also corresponds to the lower bound of the 2-sided 96.4% CI for VE being $> 20\%$. If there is failure to reject the hypothesis H_{03} , the hypothesis test H_{02} will not be performed.

The statistical analysis specifications for the primary endpoints are summarized in Table 6.

Table 6. Statistical Analysis Specifications for the Primary Endpoints

Primary Endpoints	Time Period for Case Accrual	CDI Case Definition	Analysis Population	Hypothesis Testing ^a	Statistical Testing Method

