9.5. Interim Analysis

Three (3) planned formal interim analyses will be performed by the independent statistical team (IST) to assess whether there is overwhelming efficacy or futility with respect to the end-of-study success criterion.

The first, second, and third interim analyses are planned after 30, 40, and 50 first primary CDI cases have occurred from 14 days after receipt of the third dose of investigational product, respectively. The data cutoff date will be the calendar date of the confirmed 30th, 40th, or 50th cases of first primary CDI occurring 14 days after the third dose by the central laboratory. Only the first primary efficacy endpoint will be examined. The statistical hypotheses testing (H_{03}) will be performed on interim data; H_{02} will be tested if H_{03} is rejected and a decision is made to proceed the final analysis

The early efficacy stopping boundary is derived on a GS design⁶⁵ (utilizing a single-binomial distribution, conditional on the total number of 66 cases, with 3 interim analyses at 45% [30 out of 66], 61% [40 out of 66], and 76% [50 out of 66] of information and a gamma[-2] alpha spending function).

The GS design from EAST (software package for clinical trial design) is based on normal approximation to binomial distribution, and EAST was used as a starting point to calculate GS design boundaries. Those were later converted into discrete boundaries (expressed as numbers of cases rather than proportions of cases coming from a vaccine group, given the total number of cases).

If there are 6 or fewer cases observed in the *C difficile* vaccine group out of a total of 30 first primary cases (point estimate of VE $\geq 75.0\%$ and corresponding to a lower bound of 2-sided 98.8% exact CI $>20\%$), the null hypothesis in H_{03} will be rejected, the *C difficile* vaccine will be deemed efficacious, and a full analysis of the data will be conducted.

If there are 9 or fewer cases observed in the *C difficile* vaccine group out of a total of 40 first primary cases in the second interim analysis (point estimate of VE $\geq 71.0\%$ and corresponding to a lower bound of 2-sided 98.8% exact CI $>20\%$), the null hypothesis in H_{03} will be rejected, the *C difficile* vaccine will be deemed efficacious, and a full analysis of the data may be conducted.

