If there are 13 or fewer cases observed in the *C difficile* vaccine group out of a total of 50 first primary cases in the third interim analysis (point estimate of VE $\geq 64.9\%$ and corresponding to a lower bound of 2-sided 98.2% exact CI $>20\%$), the null hypothesis in H_{03} will be rejected, the *C difficile* vaccine will be deemed efficacious, and a full analysis of the data may be conducted.

Of note, using the lower bound of a 2-sided 98.8% CI corresponds to $\alpha=0.006$ (one-sided) used for the first and second interim analyses; the lower bound of a 2-sided 98.2% CI corresponds to $\alpha=0.009$ (one-sided) for the third interim analysis.

The probabilities of stopping the trial for success are 44.3% at interim analysis 1 (ie, observe ≤ 6 cases in the *C difficile* vaccine group), 15.0% at interim analysis 2 (ie, observe ≤ 9 cases in the *C difficile* vaccine group), and 17.1% at interim analysis 3 (ie, observe ≤ 13 cases in the *C difficile* vaccine group) if the true VE is 70%.

Study futility at each interim analysis will be evaluated based on the pre-identified case split (*C difficile* vaccine vs placebo) by analysis of conditional power (CP) approach. The conditional probability of study success at the final analysis with observed VE of at least 59.6% (19 out of 66 cases) is calculated based on an assumed case split in the *C difficile* vaccine group and the assumption that an adjusted true VE of 66.5% remains for the rest of the study. The case split for futility is 11 versus 19 for IA1 (corresponding to a CP cutoff of 50% at 30 cases), 13 versus 27 for IA2 (corresponding to a CP cutoff of 60% at 40 cases), and 16 versus 34 for IA3 (corresponding to a CP cutoff of 60% at 50 cases).

These futility boundaries may be subject to change to reflect subsequent program-related decisions by the Sponsor.

The probability of stopping the trial because of futility is 6.6% at interim analysis 1 (ie, observe ≥ 11 cases in the *C difficile* vaccine group), 5.8% at interim analysis 2 (ie, observe ≥ 13 cases in the *C difficile* vaccine group), and 2.0% at interim analysis 3 (ie, observe ≥ 16 cases in the *C difficile* vaccine group), if the true VE is 70%.

The overall probability of success is at least 84.8% if the true VE is 70%.

Additional futility assessments for the study might be carried out at the time of external data monitoring committee (E-DMC) meetings. Full details of the futility assessment will be provided in the SAP.

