There is no impact on the overall type I error rate for futility analyses performed for the study.

Additional design operating characteristics (stopping boundary based on the number of cases observed in the *C difficile* vaccine group; the probabilities of stopping for efficacy and futility given assumed various VEs with a 1:1 randomization ratio) are listed in Table 7.

Table 7. Statistical Design Operating Characteristics

	Interim Analysis #1 (Total Cases = 30)		Interim Analysis #2 (Total Cases = 40)		Interim Analysis #3 (Total Cases = 50)		Final Analysis (Total Cases = 66)		
Vaccine Efficacy (%)	Probability of Success (Cases in C difficile Vaccine Group ≤ 6)	Probability of Failure (Cases in C difficile Vaccine Group ≥ 11)	Probability of Success (Cases in C difficile Vaccine Group ≤ 9)	Probability of Failure (Cases in C difficile Vaccine Group ≥ 13)	Probability of Success (Cases in C difficile Vaccine Group ≤ 13)	Probability of Failure (Cases in C difficile Vaccine Group ≥ 16)	Probability of Success (Cases in C difficile Vaccine Group ≤ 20)	Probability of Failure (Cases in C difficile Vaccine Group ≥ 21)	Overall Probability of Success
0	0.0007	0.9506	0.0002	0.0416	0.0003	0.0050	0.0002	0.0014	0.0014
20	0.0047	0.8512	0.0017	0.1066	0.0029	0.0211	0.0033	0.0085	0.0126
50	0.0838	0.4152	0.0397	0.2032	0.0721	0.0709	0.0739	0.0410	0.2696
60	0.2039	0.2146	0.0909	0.1490	0.1424	0.0557	0.1134	0.0300	0.5507
70	0.4427	0.0656	0.1496	0.0583	0.1711	0.0202	0.0845	0.0080	0.8479
80	0.7765	0.0067	0.1207	0.0063	0.0730	0.0015	0.0149	0.0003	0.9852

Note: Assumes 95.7% assay sensitivity and 99.1% assay specificity. Assumes equal follow-up times between vaccine groups.

Should the actual amount of information observed at interim analysis be more than the planned information capture for each interim analysis, the first targeted primary cases will be used for the analysis.

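### The stated 89.8% power at adjusted VE 66.5% is not what the stopping rules give: 75.5% with futility followed, 87.6% with it ignored

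*Protocol*

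**What the plan says.** Protocol Section 9.1 sets the design assumption, "With assumptions of a true adjusted VE of 66.5% after 3 doses of investigational product", and states that 66 first primary cases in the per-protocol-3 population "will provide 89.8% power to conclude true VE of >20%, taking into consideration 3 interim analyses". It refers the reader to Section 9.5 for those interim analyses.

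Section 9.5 gives each interim analysis an efficacy boundary and a futility boundary, both as counts of cases in the vaccine group. It explains that the design software works by normal approximation and served as a starting point: "Those were later converted into discrete boundaries". For VE 70% it adds: "The overall probability of success is at least 84.8% if the true VE is 70" (per cent).

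Protocol Table 7 and SAP Table 27 list success and failure probabilities at VE 0, 20, 50, 60, 70 and 80%. Neither has a row for 66.5%, the value on which the design rests.

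**The concern.** The chance of success rises with true VE. If it is 84.8% at VE 70% under the Section 9.5 rules, it cannot be 89.8% at 66.5% under those same rules. Either the two figures rest on different, unlabelled bases or one of them is wrong.

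This is the headline power for H03, the hypothesis that defines study success. It also accompanies the move from a design with 106 cases and 90% power to one with 66 cases. A figure of 89.8% makes that move look almost free in power. If the true figure is lower, anyone who relied on Section 9.1 accepted a larger risk of missing an effective vaccine than they were told.

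**Working it through.** **Inputs**

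- Design VE 66.5%, 66 cases, 1:1 allocation (Protocol 9.1).
- Null hypothesis VE ≤ 20%, one-sided (Protocol 9.2.1).
- Equal follow-up (Table 7 note: "Assumes equal follow-up times between vaccine groups").
- Success: ≤6 of 30, ≤9 of 40, ≤13 of 50, ≤20 of 66 vaccine-group cases (Protocol 9.2.1 and 9.5).
- Futility: ≥11 of 30, ≥13 of 40, ≥16 of 50 (Protocol 9.5).
- Gamma(−2) spending (Protocol 9.1 and 9.5) of one-sided alpha 0.025 (SAP 5.1.2).

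**Step 1. Vaccine share of cases.** With equal follow-up, each case falls in the vaccine group with probability p = (1 − VE)/(2 − VE).

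- Null, VE 20%: p0 = 0.8/1.8 = 0.4444
- Design, VE 66.5%: p1 = 0.335/1.335 = 0.2509
- VE 70%: p = 0.30/1.30 = 0.2308

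**Step 2. Where 89.8% probably comes from.** Cumulative alpha is 0.025 × (1 − e^(2t))/(1 − e^2) at t = 30/66, 40/66, 50/66 and 1, which gives 0.0058, 0.0092, 0.0139 and 0.0250. The matching nominal one-sided levels are 0.0057, 0.0060, 0.0088 and 0.0180, in line with the documented 0.006, 0.006, 0.009 and 0.018. The statistic is z = (n·p0 − x)/√(n·p0(1 − p0)), where x is the vaccine-group count; its distribution under the design VE uses p1(1 − p1) for the variance. With efficacy boundaries only, power is 89.6% (4 million simulated paths), within 0.2 points of the stated 89.8%.

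On the count scale these boundaries are 6.45, 9.89, 13.89 and 20.87 cases. The protocol's whole-number rules are 6, 9, 13 and 20, each rounded down, so each is stricter.

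**Step 3. Exact recursion with the documented rules.** At 30 cases the count is Binomial(30, p). Probability at or below the efficacy boundary counts as success, and at or above the futility boundary as failure. The rest (7–10 cases) is carried forward and combined with Binomial(10, p) to reach 40 cases (continue on 10–12), Binomial(10, p) to reach 50 (continue on 14–15), and Binomial(16, p) to reach 66.

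*Check against the protocol at VE 70%:* 0.4427 + 0.1496 + 0.1711 + 0.0845 = 0.8479, as in Table 7. The other rows also match, so this is the protocol's own method.

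*At VE 66.5%:*

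| Look | Success | Failure |
|---|---|---|
| 30 cases | 0.3437 | 0.1080 |
| 40 cases | 0.1326 | 0.0895 |
| 50 cases | 0.1738 | 0.0325 |
| 66 cases | 0.1049 | 0.0150 |
| **Total** | **0.7550** | **0.2450** |

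Interim futility stops account for 0.1080 + 0.0895 + 0.0325 = 0.2300 of the failures.

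*Futility boundaries removed:* success at VE 66.5% is 0.8761.

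**Step 4. Comparison**

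| True VE | Futility followed | Futility ignored |
|---|---|---|
| 66.5% | 75.5% | 87.6% |
| 68% | 79.7% | 90.7% |
| 70% | 84.8% | 93.9% |

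- Gap to the stated power: 89.8 − 75.5 = 14.3 points, or 89.8 − 87.6 = 2.2 points.
- Cost of the futility rules at the design VE: 87.6 − 75.5 = 12.1 points.
- VE needed for 89.8%: about 72.4% with futility followed, about 67.6% with it ignored.

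**The case against.** The strongest reply is that futility is discretionary. The Protocol Summary says it may be declared, Section 9.5 lets the sponsor change the boundaries, and Section 9.6 leaves the final decision with the sponsor. On that view 75.5% is the extreme case, the fair comparison is 87.6%, and the remaining 2.2 points are a rounding effect of a disclosed approximation. The wording for VE 70%, at least 84.8%, also reads like a lower bound with futility followed; without futility it would be 93.9%, so 89.8% at 66.5% would not break the ordering. Part of this stands: the larger gap does depend on the futility rule being followed. But 87.6% is the ceiling for these whole-number boundaries and still falls short of 89.8%. Section 9.1 refers to the Section 9.5 interim analyses, which include futility, and both operating-characteristics tables count futility crossings as failures.

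A second reply is that SAP version 4 now stops the study with at least 40 cases, so the 66-case power no longer describes the final analysis. That is true and limits the practical consequence. It does not correct the protocol, and SAP Sections 2.2.1 and 2.2.2 still state the 66-case target.

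Third, the protocol does not say that 89.8% was the reason for the smaller target. It cites a revised VE assumption and the blinded disease rate. That is accepted.

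Finally, the Table 7 note says assay sensitivity and specificity are assumed, yet the table reproduces with its VE column used directly. The contradiction survives either reading, because 70% exceeds both the adjusted 66.5% and the unadjusted 68%.

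**Conclusion.** The stated power is wrong for the design as written. At adjusted VE 66.5% with equal follow-up, the documented boundaries give 75.5% if every futility crossing ends the study and 87.6% if none does; no exact reading gives 89.8%. The risk of missing a vaccine that performs as assumed is 24.5% or 12.4% respectively, against the implied 10.2%.

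About 2 points of the shortfall come from the whole-number boundaries and about 12 from futility. That 89.8% was carried over from the normal-approximation stage is an inference from the 89.6% match; the finding does not depend on it. The tabulated values in Table 7 and SAP Table 27 are correct for the VE shown. The fault lies in Section 9.1 and in the missing row. This should be corrected, because it is the main power statement for the hypothesis that defines success.

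**What to change.** 1. In Protocol Section 9.1, replace 89.8% with the exact figures at adjusted VE 66.5%: 75.5% with the futility boundaries followed, 87.6% if they are overridden. Say that both use the whole-number boundaries.
2. Add a 66.5% row to Protocol Table 7 and SAP Table 27, success/failure at each look: 0.3437/0.1080, 0.1326/0.0895, 0.1738/0.0325, 0.1049/0.0150, overall success 0.7550. In the SAP the row documents the plan in force before the December 2021 letter.
3. In Section 9.5, label the 84.8% at VE 70% as the figure with futility followed.
4. Reconcile the assay note under Table 7, which SAP Table 27 lacks, so that it is clear whether the VE column is adjusted.

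The cost is a few sentences and one table row. The stated power becomes less favourable; no patients, boundaries, alpha levels or procedures change.
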